10.4 Primary objective

Part 1: Safety run-in

The primary objective is to determine the recommended regimen of PDR001 in combination with dabrafenib and trametinib for the randomized part (part 3)

Part 2: Biomarker cohort

The primary objective is to evaluate changes in PD-L1 levels and CD8+ cells upon treatment with PDR001 in combination with dabrafenib and trametinib.

Part 3: Double-blind, randomized, placebo-controlled part

The primary objective is to evaluate and compare PFS per RECIST 1.1 of PDR001 in combination with dabrafenib and trametinib versus dabrafenib and trametinib plus placebo.

10.4.1 Variables

Part 1: Safety run-in

The primary variable is the incidence of DLTs during the first 8 weeks (56 days) of treatment for each dose level associated with administration of PDR001 in combination of dabrafenib and trametinib.

Part 2: Biomarker cohort

The primary variable is PD-L1 levels and CD8+ cells and changes from baseline.

Part 3: Double-blind, randomized, placebo-controlled part

The primary efficacy variable is PFS, defined as the time from the date of randomization to the date of the first documented progression per RECIST 1.1 or death due to any cause. PFS will be assessed via local review according to RECIST 1.1 (see [Appendix 1](#) for further details). Censoring conventions are provided below in [Section 10.4.3](#).

Local scans will be sent to a blinded, independent central reviewer who will provide assessments using both RECIST 1.1 and tumor response criteria based on guidelines for immunotherapy, and these centrally reviewed data will be used for sensitivity analysis.

10.4.2 Statistical hypothesis, model, and method of analysis

Part 1: Safety run-in

Identification of recommended regimen

Estimation of the recommended regimen will be based upon the estimation of the probability of DLT in the first 8 weeks (56 days) for subjects in the DDS. A lower recommended regimen may be identified based on other safety and PK data from the current study ([Section 6.2.3](#)).

Bayesian adaptive approach

The dose determination part of this study will be guided by a Bayesian analysis of DLT data for the first 8 weeks (56 days) that subjects receive the combination of PDR001, dabrafenib, and trametinib. The Bayesian analysis to assess the triple combination will be based on a separate 10-parameter model for each dose regimen that comprises single-agent toxicity parts and interaction parts to describe both two-way and three-way drug safety interactions. Single agent toxicity is modelled using logistic regression for the probability of a subject experiencing a DLT against log-dose. The odds of a DLT for each dose regimen are then calculated under no interaction for the three single agent toxicities, and interaction is accounted for by adjusting these odds with additional model parameters (odds multipliers). Details of the model are given in [Appendix 2](#).

Assessment of subject risk

After each cohort of subjects, the posterior distribution for the risk of DLT for new subjects at combination doses of interest will be evaluated. The posterior distributions will be summarized to provide the posterior probability that the risk of DLT for each dose regimen lies within the following intervals:

- Under-dosing: [0, 16%)
- Targeted toxicity: [16%, 33%)
- Excessive toxicity: [33%, 100%]

The escalation with overdose control (EWOC) principle

Dosing regimen decisions are guided by the escalation with overdose control principle (Rogatko 2007). A dosing regimen may only be used for newly enrolled subjects if the risk of excessive toxicity at that dosing regimen is less than 25%.

Prior distributions

A meta-analytic-predictive (MAP) approach was used to derive the prior distribution for the single-agent PDR001, dabrafenib, and trametinib model parameters. The MAP prior for the logistic model parameters for this study is the conditional distribution of the parameters given the historical data (Spiegelhalter 2004, Neuenschwander 2010, Neuenschwander 2014). MAP priors are derived from hierarchical models, which take into account possible differences between the studies. For dabrafenib and trametinib, 100% MAP priors will be used. For PDR001, this is then robustified by creating a mixture prior including both a component derived from the MAP prior and a weakly informative robustification component. This robustification allows for the possibility that the dose/toxicity relationship for PDR001 in combination differs substantially from that of the single agent. A full description of the application of the MAP approach to derive the prior distributions of the single agent PDR001, dabrafenib, and trametinib model parameters for each dose regimen is given in [Appendix 2](#).

The prior distributions for the interaction parameters were based upon prior understanding of possible drug safety interactions. These priors allow for the possibility of either synergistic or antagonistic interaction, and are fully described in [Appendix 2](#).

Additional DLT information from completed studies assessing the combination of dabrafenib and trametinib (i.e. Phase I study BRF113220, Phase III study MEK115306 (COMBI-d), and Phase III study MEK116513 (COMBI-v)) are included using discounted weighting. Full details of the discounted weighting approach are described in [Appendix 2](#).

Starting dose

The starting dosing regimen is 400 mg i.v. Q4W PDR001, 150 mg BID dabrafenib, and 2 mg QD trametinib ([Section 6.2.1](#)). For this dosing regimen, the prior risk of excessive toxicity is 12%, which satisfies the EWOC criterion. A full assessment of the prior risk to subjects for all dosing regimens is given in [Appendix 2](#). Historical data were reviewed to account for modified DLT criteria (protocol amendment 2). Prior specifications for the BLRM were not impacted, and therefore the starting dose of Part 1 remained unchanged.

Listing of DLT's

DLTs will be listed, and their incidence summarized by primary system organ class and preferred term and worst grade (CTCAE v4.03). Listings and summaries will be based on the DDS.

Part 2: Biomarker cohort

Descriptive statistics of the primary endpoint, PD-L1 levels and CD8+ cell values and changes from baseline, will be summarized by visit.

Part 3: Double-blind, randomized, placebo-controlled part

The following statistical hypotheses will be tested to address the primary efficacy objective for PFS (based on investigator assessment of RECIST 1.1 criteria):

$$H_{01} : \theta_1 \geq 1 \text{ vs. } H_{A1} : \theta_1 < 1$$

where θ_1 is the PFS hazard ratio (PDR001 combined with dabrafenib and trametinib versus dabrafenib and trametinib plus placebo). The primary efficacy analysis to test these hypotheses and compare the two treatment groups will consist of a stratified log-rank test at an overall one-sided 2.5% level of significance. The stratification will be based on the randomization stratification factors, i.e., (LDH level: $< 1 \times \text{ULN}$ vs ≥ 1 to $< 2 \times \text{ULN}$ vs $\geq 2 \times \text{ULN}$; ECOG PS: 0 vs 1 vs 2).

Analyses will be based on the FAS population according to the randomized treatment group and strata assigned at randomization. The PFS distribution will be estimated using the Kaplan-Meier method, and Kaplan-Meier curves, quartiles and associated 95% confidence intervals will be presented for each treatment group. The hazard ratio for PFS will be calculated, along with its 95% confidence interval, from a stratified Cox model using the same stratification factors as for the log-rank test.

The PFS analysis will be performed as part of a two-look group sequential design using a conservative Gamma alpha spending function with Gamma parameter = -9.7 (Hwang, Shih and DeCani, 1990). Analyses will be based on the FAS population according to the randomized treatment group and strata assigned at randomization. The PFS distribution will be estimated using the Kaplan-Meier method, and Kaplan-Meier curves, quartiles and associated 95% confidence intervals will be presented for each treatment group. The hazard ratio for PFS will be calculated, along with its 95% confidence interval, from a stratified Cox model using the same stratification factors as for the log-rank test.

If the interim PFS analysis is significant, the subsequent planned final PFS analysis will still be performed to obtain more mature PFS data and additional follow-up PFS analyses may also be performed earlier than planned final PFS analysis at the request of health authorities or to facilitate health authority interactions.

The data cutoff date for the final PFS analysis will occur at the time when the target number of approximately 352 PFS events has been observed or at approximately 24 months after the last patient has been randomized, whichever occurs first.

10.4.3 Handling of missing values/censoring/discontinuations

Part 1: Safety run-in

Subjects who are ineligible for the DDS will be excluded from the primary analysis (incidence of DLT during first 8 weeks of PDR001 in combination with dabrafenib and trametinib), although their data will be used for all remaining analyses.

Other missing data will simply be noted as missing on appropriate tables/listings.

Part 2: Biomarker cohort

Missing data will simply be noted as missing on appropriate tables/listings.

Part 3: Double-blind, randomized, placebo-controlled part

In the primary analysis, PFS will be censored at the date of the last adequate tumor assessment if no PFS event is observed prior to the analysis cut-off date.

PFS events documented after the initiation of new anti-neoplastic therapy (i.e. RECIST 1.1 documented disease progression or death) will be considered for the primary analysis provided tumor assessments continue after initiation of new cancer therapy.

If a PFS event is observed after two or more missing or non-adequate tumor assessments, then PFS will be censored at the last adequate tumor assessment before the PFS event. If a PFS event is observed after a single missing or non-adequate tumor assessment, the actual date of event will be used (RECIST 1.1 in [Appendix 1](#)).

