7.1.7 Follow up for efficacy evaluations -

Prior to the final PFS analysis (not applicable after primary end point interim analysis):

All subjects who discontinue study treatment without disease progression by RECIST 1.1 will continue tumor assessments as outlined in [Section 7.1](#) until documented disease progression by RECIST 1.1, withdrawal of consent, lost to follow-up, or death irrespective of start of new anti-neoplastic therapy.

All subjects who continue treatment beyond disease progression per RECIST 1.1 (see [Section 6.1.5.1](#)) will continue tumor assessments as outlined in [Section 7](#) until confirmed progression per response criteria for immunotherapy, unacceptable toxicity, start of new anti-neoplastic therapy, withdrawal of consent, physician's decision, lost to follow-up, death or study is terminated by sponsor.

Refer to [Section 7.2.1.2](#) for details on additional tumor assessments that should be performed to confirm response or allow for further central analysis.

Following the final PFS analysis:

Efficacy data, other than overall survival, will no longer be collected.

All subjects who discontinue study treatment will immediately be followed for safety assessments and as part of the overall survival follow-up until death, lost to follow-up, or withdrawal of consent as described in [Section 7](#).

There will not be an efficacy follow-up phase. Standard local medical practice may be applied for tumor assessment. There is no requirement to record any tumor assessment results in the eCRF and imaging data must not be sent to the central imaging vendor.

Additional required data will be collected such as post-treatment anti-neoplastic therapies. See [Section 7.2.1](#) for further details.

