Overall response rate (ORR) is defined as the proportion of subjects with confirmed best overall response (BOR) of complete response (CR) or partial response (PR), as per local review. ORR will be evaluated according to RECIST 1.1 ([Appendix 1](#)). Complete and partial responses must be confirmed by repeat assessments that should be performed not less than 4 weeks after the criteria for response are first met. ORR based on local review will be calculated based on the FAS. ORR and its 95% confidence interval will be presented by treatment group. The Cochran-Mantel-Haenszel chi-square test, stratified by the randomization stratification factors, will be used to compare ORR between the two treatment groups, at the one-sided 2.5% level of

significance. As a supportive analysis, ORR as per blinded independent central review (using RECIST 1.1 as well as tumor response criteria based on guidelines for immunotherapy) will be presented by treatment group, along with 95% confidence intervals.

Duration of response (DOR) only applies to subjects whose best overall response is complete response (CR) or partial response (PR) based on tumor response data per local review. DOR will be evaluated according to RECIST 1.1 ([Appendix 1](#)). The start date is the date of first documented response of CR or PR (i.e., the start date of response, not the date when response was confirmed), and the end date is defined as the date of the first documented progression or death due to underlying cancer. Subjects continuing without progression or death due to underlying cancer will be censored at the date of their last adequate tumor assessment. DOR based on RECIST 1.1 will be listed and summarized by treatment group for all subjects in the FAS with confirmed BOR of CR or PR, as well as for the subgroup of FAS subjects with confirmed BOR of CR only.

DCR is defined as the proportion of subjects with CR or PR or subjects with stable disease (SD) lasting for a duration of at least 24 weeks as per local review. CR, PR and SD are defined according to RECIST 1.1 (see [Appendix 1](#) for details). DCR will be calculated based on the FAS. DCR and its 95% confidence interval will be presented by treatment group. As a supportive analysis, DCR as per blinded independent central review (using RECIST 1.1 as well as tumor response criteria based on guidelines for immunotherapy) will be presented by treatment group, along with 95% confidence intervals.

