Situation F: New cancer therapy given: the handling of this situation must be specified in detail in the protocol. However, option (1) (ITT) is the recommended approach; events documented after the initiation of new cancer therapy will be considered for the primary analysis i.e. progressions and deaths documented after the initiation of new cancer therapy would be included as events. This will require continued follow-up for progression after the start of the new cancer therapy. In such cases, it is recommended that an additional sensitivity analysis be performed by censoring at last adequate assessment prior to initiation of new cancer therapy.

Option (2), i.e. censoring at last adequate assessment may be used as a sensitivity analysis. If a high censoring rate due to start of new cancer therapy is expected, a window of approximately 8 weeks performed after the start of new cancer therapy can be used to calculate the date of the event or censoring. This should be clearly specified in the SAP.

In some specific settings, local treatments (e.g., radiation/surgery) may not be considered as cancer therapies for assessment of event/censoring in PFS/TTP/DoR analysis. For example, palliative radiotherapy given in the trial for analgesic purposes or for lytic lesions at risk of fracture will not be considered as cancer therapy for the assessment of BOR and PFS analyses. The protocol should clearly state the local treatments which are not considered as antineoplastic therapies in the PFS/TTP/DoR analysis.

The protocol should state that tumor assessments will be performed every x weeks until radiological progression irrespective of initiation of new antineoplastic therapy. It is strongly recommended that a tumor assessment is performed before the patient is switched to a new cancer therapy.

Additional suggestions for sensitivity analyses

Other suggestions for additional sensitivity analyses may include analyses to check for potential bias in follow-up schedules for tumor assessments, e.g., by assigning the dates for censoring and events only at scheduled visit dates. The latter could be handled by replacing in [Table 14-4](#) the “Date of last adequate assessment” by the “Date of previous scheduled assessment (from baseline)”, with the following definition:

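### Read literally, the new-therapy proviso in Section 10.4.3 censors deaths that the primary PFS definition counts as events

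*Protocol*

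**What the plan says.** Section 10.4.1 defines PFS as time from randomization to "the first documented progression per RECIST 1.1 or death due to any cause". It attaches no condition about scans to the death component.

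Section 10.4.3 sets the censoring rules for the primary analysis:

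- Events after a new anti-neoplastic therapy, which the text spells out as RECIST progression or death, "will be considered for the primary analysis provided tumor assessments continue after initiation of new cancer therapy".
- If the event follows two or more missing or non-adequate assessments, "then PFS will be censored at the last adequate tumor assessment before the PFS event".
- Where only one assessment was missed or inadequate, by contrast, the event stands and "the actual date of event will be used".

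Appendix 1 treats new therapy as situation F (Section 14.1.3.2.8, Table 14-4). Its default is to ignore the new therapy, and the explanatory text says that "progressions and deaths documented after the initiation of new cancer therapy would be included as events". Below the table, it asks the protocol to say whether and why the default is not used for situation F.

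Section 7.1.7 plans for scans to go on after a switch. For patients who stop treatment without progression they run until progression, "withdrawal of consent, lost to follow-up, or death irrespective of start of new anti-neoplastic therapy".

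**The concern.** The proviso is sensible for progression, which cannot be documented without a scan. A death needs no scan, and its date is collected for overall survival anyway. Because the sentence names death within the condition, it can be programmed so that a death after a switch is an event only if scans carried on.

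Patients who switch without RECIST progression and stop being scanned are plausibly a poor-prognosis group, so censoring them just before death would be informative. A practical problem comes with it: what it means for assessments to continue is not defined. Two programmers working from Section 10.4.3 could derive different primary datasets.

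**Working it through.** **Step 1: the plan's own figures.** Inputs from Sections 10.7.1 and 10.8: 352 events, average HR 0.739, 1:1 allocation, one-sided 2.5%, interim at 260 events, gamma -9.7.

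- Interim information fraction: 260/352 = 0.7386. Hwang-Shih-DeCani spending: 0.025 × (1 − e^(9.7 × 0.7386)) / (1 − e^9.7) = 0.00198, as stated. Solving for the final look gives p = 0.02483 and HR 0.811, as stated.
- Power (Schoenfeld) = Φ(√d/2 × |ln HR| − z). With d = 352, √352/2 = 9.381 and |ln 0.739| = 0.3025. At the final nominal level (z = 1.963) this is Φ(2.837 − 1.963) = 80.9%, against 80.6% in Table 10-1.

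The event target, power and boundaries reproduce. The sample size is not in error.

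**Step 2: the rules side by side.** Table 7-4 schedules efficacy follow-up scans every 12 weeks from the last assessment. Ignoring the ±7-day window, a death before week 24 from the last adequate scan follows at most one missed assessment. Take a patient who has switched, has no scan afterwards, and dies:

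| Death occurs | 10.4.1 definition | 10.4.3 proviso, read literally | 10.4.3 missed-assessment rules | Appendix 1 default |
|---|---|---|---|---|
| Before any scan is due | Event | Unclear; not an event on the strictest reading | Event | Event |
| After exactly one missed scan | Event | Not an event | Event | Event |
| After two or more missed scans | Event | Not an event | Censored | Censored |

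The second row is a direct conflict within Section 10.4.3. The first is an ambiguity. In the third, the proviso changes nothing, because the two-missed-assessments rule already censors.

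**Step 3: size.** The protocol gives no rate of switching, stopping scans or early death, so these are assumptions. Suppose 3 to 8% of the 532 randomized switch without RECIST progression and stop scans, and 20 to 40% of those die within two scan intervals.

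- Low: 532 × 0.03 = 16; 16 × 0.2 = 3 deaths; 3/352 = 0.9%.
- High: 532 × 0.08 = 43; 43 × 0.4 = 17 deaths; 17/352 = 4.8%.

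If the loss is equal by arm and the cutoff is not moved, at the final nominal level:

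- 1% lost: 348 events, power 80.5%.
- 5% lost: 334 events, power 78.9%.

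**Step 4: equal against unequal loss.** This is an illustrative simulation with 532 patients, an assumed 9-month accrual, dropped deaths censored 0.5 to 3.5 months early, a test at the final boundary only, and 1,500 runs per setting.

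| Events dropped, control / experimental | Mean HR, all counted → dropped | Power, all counted → dropped | One-sided type I error after dropping |
|---|---|---|---|
| 5% / 5% | 0.742 → 0.742 | 81% → 79% | 2.3% |
| 2% / 5% | 0.743 → 0.722 | 79% → 84% | 4.9% |
| 5% / 2% | 0.741 → 0.761 | 79% → 71% | 1.4% |
| 5% / 10% | 0.743 → 0.704 | 79% → 88% | 6.7% |
| 10% / 5% | 0.738 → 0.774 | 81% → 61% | 0.5% |

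Equal loss leaves the HR alone. Unequal loss moves it towards whichever arm loses more deaths. The last two rows average 7.5% of events, above the range in Step 3, and are stress cases.

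**The case against.** The strongest defence is that the proviso is shorthand for the Appendix 1 remark that counting later events requires continued follow-up, and was never meant to discard deaths. If no scan was yet due, none was missed and assessments have not stopped. Sections 7.1.7 and 7.2.1.2 and Table 7-4 keep scans going after a switch until progression, so the proviso bites only on departures from schedule. The analysis is event-driven, so lost events can be replaced until the cap of about 24 months after the last randomization. Section 10.4.4 reports censoring reasons by arm, and the SAP, not shown here, may settle the derivation.

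Most of this stands as a limit on size. It does not remove the conflict: the sentence names death, Appendix 1 makes follow-up a task and not a condition for counting a death, and the case of one missed scan has two answers in the same section.

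A reader might also infer three stronger points that the documents do not support:

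- **That PFS was biased in favour of the experimental arm.** Nothing says which arm would lose more deaths, and the simulation moves either way.
- **That type I error was inflated to 5 to 7%.** Those figures need unequal loss that is assumed, not documented.
- **That the duration-of-response rule is a second contradiction.** In Section 10.5.2 "the end date is defined as the date of the first documented progression or death due to underlying cancer", so other deaths are censored. This is a separate endpoint, summarized descriptively, and it follows Appendix 1, which ties it to time to progression and censors non-cancer deaths there. It does not contradict the PFS definition. No rate of non-cancer death among responders is given, so any overstatement cannot be sized.

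**Conclusion.** The point holds for PFS. As worded, Section 10.4.3 can censor a death after a therapy switch that Section 10.4.1, the single-missed-assessment rule and the Appendix 1 default all count, and the reason that Appendix 1 asks for is absent. The effect is probably small: about 1 to 5% of 352 events under the assumed rates, and at most about 2 power points if the loss is equal by arm and the cutoff stays put. The direction of any bias in the hazard ratio cannot be determined from the protocol. It is worth correcting because it concerns the primary endpoint and leaves its derivation open to two readings. The cancer-death rule for duration of response is a convention that could be supplemented, not an error.

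**What to change.** In Section 10.4.3, limit the proviso to RECIST progressions. State that every death is a PFS event at its actual date, with or without new therapy, unless the two-or-more-missed-assessments rule applies.

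The protocol reports that the final PFS analysis has been done and was not significant, so the clarification should not replace the primary result. The sponsor should state which rule was applied to deaths after new therapy. If it was the literal proviso, report PFS with those deaths counted as a sensitivity analysis, labelled as added after the analysis, and give the number of reclassified deaths by arm.

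For duration of response, at most add a supportive version that ends at progression or death from any cause.

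The cost is a sentence or two of text and one re-run of the PFS derivation. Death dates are already collected for overall survival, so no new data are needed.
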